6.1 Anticipated clinical benefit

Both groups will receive effective treatments.

Due to the presence of Symbiofilm®, the group receiving Healsea® Children is anticipated to recover more quickly from acute rhinitis than the group of children receiving only conventional therapies for the common cold.

6.2 Anticipated adverse device effects

The only anticipated adverse device effect is the feeling of nasal itching and irritation while initiating the treatment with the medical device Healsea® Children. In case of such adverse reaction, the parents/legal guardians/patients will be instructed to contact the investigator if the patient wishes to stop the nasal spray use.

Version: **2.0; 08 Sep 2021** Page **26** of **61**

6.3 Risks associated with participation in the clinical investigation

No design element, subject to safety-related questioning is identified. The instructions for use include mentions to control risks. Patients with known hypersensitivity/allergy to any component of the test device will not be enrolled in the study. The clinical procedures comprise daily completion of an electronic diary comprising a validated questionnaire (WURSS-K) [18] only.

6.4 Possible interactions with concomitant medical treatments as considered under the risk analysis

No interaction is expected. Nevertheless, patient will be instructed to respect a 60-minute minimum interval after administration of the investigational medical device before administration of another local medication e.g., decongestant or mucolytics (if permitted).

6.5 Steps that will be taken to control and mitigate the risks

In the line with *NF EN ISO 14971:2019* standard (Medical Devices – Application of risk management to medical devices), a risk analysis has been conducted to estimate the risks associated with each step of the device lifecycle. Most of the risk has been mitigated through product design and manufacturing.

The residual risk to patients who are administered this intervention is low. A list of potential risks associated with the device, procedures undertaken to minimise them, and methods used for their management is described in the device Risk Management Process File.

Considering:

- the risk analysis (ISO 14 971 activities) that demonstrates:
 - o There is no longer High level risk,
 - o That, the 41 Medium risk level residuals risks have an acceptable benefit-risk balance,
 - And all of the others residual risks (85) are at Low risk.
- the fact that the device Healsea® Children can be considered as safe and effective according to the Clinical Evaluation Report.

the overall residual risk is acceptable, and the benefit/risk ratio is considered satisfactory.

The verification of the implementation of risk control measures during life cycle phases of Healsea® Children is mainly performed by LALLEMAND PHARMA AG using the operating procedures currently used.

No specific risk for subject in participating in the study is identified, provided that the eligibility criteria are fulfilled. Thus, the establishment of risk acceptability thresholds is not deemed necessary although it is a requirement from the ISO 14155:2020. Nevertheless, the safety and well-being of subjects will be monitored throughout the study. Should a potential unanticipated risk be detected, the clinical investigation will be suspended, the risk assessment will be updated to adapt the risk control measures and the benefit-risk analysis.

Version: **2.0**; **08** Sep **2021** Page **27** of **61**

6.6 Rationale for the benefit-risk ratio

Although infectious rhinitis is in most cases self-limiting, it impacts the children's quality of life during generally about 7-10 days. Furthermore, bacterial over infections with worsening of symptoms can occur requiring antibiotic prescription. Progression to a chronic state, i.e., chronic rhinosinusitis is also observed.

Conventional therapies for infectious rhinitis are symptomatic and not without side effect. For example, decongestant use can increase blood pressure, antihistamine intake is associated with drowsiness.

Healsea® Children represents an interesting alternative because the nasal spray could alleviate acute infectious rhinitis symptoms but also limit the complication and progression to chronic state.

Furthermore, apart from feeling of nasal itching and irritation while initiating the treatment, no adverse effect is anticipated.

7. Objectives and hypothesis of the clinical investigation

7.1 Hypothesis

Our hypothesis is that Healsea® Children nasal spray on top of conventional therapies for common cold can improve the symptomatology of acute infectious rhinitis in allergic children (6-10 years) with more efficacy than conventional therapies only without safety concerns.

7.2 Primary Objective

To assess the impact of both treatment modalities (Healsea® Children on top of common cold conventional therapies and common cold conventional therapies only) to reduce acute infectious rhinitis symptoms in 6-10 years old allergic children during a 10-day treatment period.

7.3 Secondary Objectives

- To assess the impact of both treatment modalities to reduce the duration of each infectious rhinitis symptom as rated by the Wisconsin Upper Respiratory Symptom Survey for kids (WURSS-K) [18].
- To assess the impact of both treatment modalities to reduce complications of the acute phase during a 20-day follow-up phase.
- To assess the impact of both treatment modalities on the intake of conventional common cold medication (antibiotics, antipyretics, mucolytics, decongestants, antitussives, systemic and topical corticosteroids).

Version: **2.0**; **08** Sep **2021** Page **28** of **61**

- To assess the impact of both treatment modalities to reduce the person-to-person cold spreading among close contacts (parents, siblings).
- Safety: to assess systemic and local tolerance of Healsea® Children over the study period.

7.4 Scientific justification and clinical relevance for effect sizes, noninferiority margins or equivalence

This is a prospective, open label, observational study. An arbitrary cohort of 200 children has been chosen. A cohort of 100-exposed and 100-not exposed patients is anticipated to allow to demonstrate the interest of using Healsea® Children in the allergic paediatric population. Indeed, 100 patients by arms are enough to detect a Cohen's effect size of 0.4 with a power of 80% and a type I error of 5%. Cohen's effect size is defined as the standardized difference between AUC in groups. Following Cohen's methodology, 0.4 is an intermediate size between a small effect (0.2) and a medium effect (0.5) and is coherent with the expected result.

The recruitment will be competitive in both group, exposed to Healsea Children or not exposed to Healsea® Children. However, when 100 patients will be recruited in one group, the recruitment will be stopped in this group but will continue in the other group until 100 patients to be enrolled.

No assumption of expected outcomes across treatment group is performed.

Risks and anticipated adverse effects that are to be assessed

No specific risk for subject in participating in the study is identified, provided that the eligibility criteria are fulfilled. Nevertheless, the safety and well-being of subjects will be monitored throughout the study.

8. Design of the clinical investigation

8.1 General

8.1.1 Design type of clinical investigation

This is a prospective, open label, observational, national (Poland), multicentre study.

During this prospective observational study, one cohort of IgE-dependent allergic children with early symptoms of infectious rhinitis will be followed, children being treated with Healsea® Children on top of common cold conventional therapies or with conventional therapies only (nasal irrigation excepted). This observational study aimed to confirm the benefit of Healsea® Children in a real life setting in children with perennial allergy.

Page 29 of 61 Version: 2.0; 08 Sep 2021

8.1.2 Measures to be taken to minimize or avoid bias

Not applicable.

8.1.3 Primary Endpoint

The primary endpoint is the area under the curve (AUC) of the Wisconsin Upper Respiratory Symptom Survey for Kids (WURSS-K) during first 10 days of symptoms. AUC will be calculated applying the trapezoidal rule, with the y-axis, defined by daily WURSS-K scores, and the x-axis, defined as duration of illness, starting with the first symptoms and ending at day 10.

WURSS-K is a 3-dimensional structure questionnaire specifically designed for children 4 to 10 years of age [18] (appendix B). This survey has been demonstrated to be responsible, reliable, and valid for assessing illness specific symptoms and impact on quality of life during an acute infectious rhinitis in paediatric population.

It includes 6 items assessing symptoms (symptoms score: runny nose, stuffy nose, sneezing, sore throat, cough, feeling tired), 7 items assessing functional impairments (quality of life score: think, sleep, breathe, talk, walk/climb stairs/exercise, go to school, play with friends), 1 item assessing global severity. All these items are scored using visual representation of happy and sad faces to assist Likert scale ratings from 0 (absent or no impairment) through 1 (a little bad), 2 (bad) and 3 (very bad). The sum of the 14 items on a 4-point ordinal scale results in a global total score ranging from 0 (low symptoms and low functional impairment) to 42 (high symptoms and high functional impairment). One item assessing global change as compared to the day before is rated from 0 (a lot better) to 4 (a lot worse) is not included in the overall score.

Using an electronic diary, the patient will score the WURSS-K daily in the evening, taking in account the symptoms from the morning to the evening, during D1-D10. After D10, the WURSS-K will be assessed once daily until the subject feels not sick for two consecutive days.

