8.3.1 Eligibility criteria

8.3.1.1 Inclusion criteria

Subjects will be enrolled if they meet all of the following criteria:

- 1. Male/Female subjects ≥6 and ≤10- year old
- 2. AsIgE ≥ class 2 (RAST) or positive prick test for at least one perennial allergen
- 3. Acute infectious rhinitis/rhinosinusitis for ≤48h before trial entry
- 4. Patient presenting with fever ≥ 37.5 °C at screening
- Symptoms of headache, muscle ache, chilliness, sore throat, blocked nose, runny nose, cough, sneezing with a total score ≤9 (according to a physician-rated symptom score; scale: 0 → 3 [0: no symptom to 3: severe intensity])
- 6. At least one of these symptoms: sore throat, runny nose or blocked nose (i.e., with a score ≥1)
- 7. Written consent obtained from parent/legal guardians
- 8. Written assent obtained from patient

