8.3.11 Study procedures

The study will comprise 3 visits and 2 telephone calls.

Version: **2.0**; **08** Sep **2021** Page **34** of **61**

Visit 1 (V1) - (Day 1): Screening/Inclusion

The investigator will give oral information relative to the study to parents/legal guardians and the participant. If both parents/legal guardians agree that their child participate in the study, they will receive the information sheet and will be also asked to give a written consent. In case one parent will not be available for the visit; he/she will be asked to confirm in writing that he/she agrees with the participation of the child in the study. Children will also receive an information specific to their age and will be invited to sign an assent by the investigator.

Each screened subject will be assigned a subject identifier number during screening. The subject identifier number will contain the site number and the subject number and will be assigned in numerical order at the screening visit based on chronological order of screening dates (e.g., 01-010 for the 10th subject screened at the Site #01).

The investigator or his/her delegated designee will:

- Record demographic data and medical history and ongoing medication,
- Perform a physical and clinical examination,
- Record the score of the common cold symptoms (headache, muscle ache, chilliness, sore throat, blocked nose, runny nose, cough, sneezing according a physician-rated symptom score after clinical examination of the child; (scale: 0 3 [0: no symptom, 1 = mild symptoms (sign/symptom clearly present, but minimal awareness; easily tolerated), 2 = moderate symptoms (definite awareness of sign/symptom that is bothersome but tolerable), 3 = severe symptoms (sign/symptom that is hard to tolerate; causes interference with activities of daily living and/or sleeping]). This scoring system was developed by Jackson in 1958 and is widely used in common cold clinical trials [19],
- Verify that eligibility criteria are fulfilled,
- Record the patient choice regarding Healsea® Children use (if the patient/parents choose nasal symptoms to be treated with Healsea® Children, instructions will be given to the patient/parents for getting the test product at the end of the visit),
- Explain to the child/parents/legal guardians how to use Healsea® Children if applicable,
- Review and detail the questions of the WURSS-K,
- Explain how to use the e-diary for WURSS-K recording, how to report adverse events/

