6.4. General conventions and calculated variables**6.4.1. Subject reference start/end dates**

For each subject, the reference dates will be the following:

- The reference start date is the date of inclusion visit.
- The reference end date is the date when subject was determined to have ended the trial.

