6.4.6. AUC on total score of WURSS-K questionnaire

The computation of the AUC will be made for patients with non-missing value at D1 and at least another non-missing time point between D2 and D11. Otherwise, the AUC will be missing.

The AUC will be computed by the trapezoidal rule from D1 to D10 (Acute Phase).

If the value at D10 is missing:

- If there is no follow-up for the patient or if the value at D11 (the first day of Follow-up) is missing, then the value at D10 will be estimated by the value at the last non-missing time point before D10;
- If the value at D11 is not missing, the value at D10 will be estimated by a linear regression between the last non-missing time point before D10, noted Dj, and D11:

$$\text{WURSS}_{\text{TOT, EST}}(\text{D10}) = [\text{WURSS}_{\text{TOT}}(\text{Dj}) + (10 - j) \times \text{WURSS}_{\text{TOT}}(\text{D11})] / (11 - j)$$

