10. EFFICACY

10.1. Analysis of the primary efficacy criterion

The primary objective will be analysed by performing a t-test (or a Wilcoxon test if the normality assumption is not acceptable) between the means AUC of WURSS-K score during first ten days of symptoms in each group.

The answers of the fourteen first items of the WURSS-K questionnaire are scored **from 0 to 3** (0: negative answer; from 1 to 3: positive answer with an increasing severity level). See the daily symptom report in appendix (§13.3).

The total WURSS-K score at each time point is the sum of the scores of the fourteen first items of the WURSS-K questionnaire:

$$\text{At each time point } t: \text{WURSS}_{\text{tot}}(t) = \sum_{j \in \{1, \dots, 14\}} \text{WURSS}_j(t)$$

AUC of WURSS-K score will be computed by the method described in §6.4.6.

Subjects will be analysed on the Full Analysis Set and the Per-Protocol Set.

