10.2. Analysis of the secondary efficacy criteria

The analysis of the secondary endpoints will involve multivariate analysis.

The selection of variables in multivariate analysis will be performed using a 0.20 significance level and a stepwise method. Whole the multivariate analyses specified below involve the treatment and, in order to adjust for confounding, all the potential confounding factors as explanatory variables:

- Temperature at baseline (°C);
- Symptoms' scores at baseline.

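### The primary AUC is defined from first symptoms but computed from inclusion, up to 48 h later, and time since onset enters no analysis, so unequal delay between the self-chosen groups would shift the comparison

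*Protocol*

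**What the plan says.** Protocol 8.1.3 puts daily WURSS-K scores on the y-axis of the AUC, against an "x-axis, defined as duration of illness, starting with the first symptoms and ending at day 10". SAP 10.1 keeps an onset-based label, comparing the "means AUC of WURSS-K score during first ten days of symptoms in each group".

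The calculation starts elsewhere. SAP 6.4.6 states: "The AUC will be computed by the trapezoidal rule from D1 to D10 (Acute Phase". Protocol 8.3.11 heads the first visit "Visit 1 (V1) - (Day 1): Screening/Inclusion", and SAP 6.4.1 agrees: "The reference start date is the date of inclusion visit". The e-diary is explained at that visit and scored from D1. Inclusion criterion 3 in Protocol 8.3.1.1 admits children with "Acute infectious rhinitis/rhinosinusitis for ≤48h before trial entry".

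The primary analysis consists of "performing a t-test (or a Wilcoxon test if the normality assumption is not acceptable) between the means AUC of WURSS-K score", without covariates. For the secondary models, SAP 10.2 names two potential confounders under a stepwise rule: "Temperature at baseline (°C"), and the baseline symptom scores. SAP 8.4 describes the same two at baseline. Onset date or time is not among the items that Protocol 8.3.11 lists for recording at V1. SAP section 12, on changes to the planned analysis, covers only symptom duration.

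**The concern.** There are two linked problems.

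**Definition.** The window promised in the protocol begins before the first score can exist. D1-D10 covers illness days 1-10 for a child seen at onset and about days 3-12 for a child seen at 48 h. A report that speaks of the first ten days of symptoms would describe something that was not measured.

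**Comparability.** The groups are formed by family choice. Protocol 8.3.3 describes two routes into the study: children who present as outpatients, and children of pre-informed families who are invited to make contact when symptoms start. If mean time from onset to D1 differs between the groups, the AUC compares different stretches of a self-limiting illness. Part of any difference would then come from timing, and the one test that SAP 6.3.1 treats as conclusive makes no adjustment for it.

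**Working it through.** **1. The plan's own figure.** For d = 0.4, 80% power and two-sided 5%, n per group = 2(1.960 + 0.842)²/0.4² = 98.1, so 99. The exact t-test gives n = 99.1 and a power of 80.4% at 100 per group. The stated 100 per group is reproduced and is not in question.

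**2. AUC as a function of delay.** Let f(t) be the mean score t days after onset and s the delay from onset to D1. With ten daily scores,

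AUC(s) = Σ [f(s+k) + f(s+k+1)]/2, for k = 0 to 8.

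One extra day of delay changes it by

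AUC(s+1) − AUC(s) = [f(s+9) + f(s+10)]/2 − [f(s) + f(s+1)]/2.

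Later entry therefore lowers the AUC when scores around entry exceed scores nine days later, and raises it otherwise.

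**3. Illustrative curves.** Only the 0-42 score range (Protocol 8.1.3) and a course of about 7-10 days (Protocol 6.6) come from the documents. The shapes and the peak of 16 are assumptions. There is no treatment effect. Worked case, first row: [1.6 + 0]/2 − [16 + 14.4]/2 = 0.8 − 15.2 = −14.4, so 79.2 becomes 64.8.

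| Assumed course | AUC at 0 h | 24 h | 48 h | Change at 24 h / 48 h |
|---|---|---|---|---|
| 16 at onset, linear to 0 at day 10 | 79.2 | 64.8 | 51.2 | −18% / −35% |
| 8 rising to 16 at day 2, 0 at day 10 | 87 | 78 | 64 | −10% / −26% |
| 8 rising to 16 at day 2, 0 at day 7 | 64 | 54 | 40 | −16% / −38% |
| Exponential decay, 16·exp(−t/4) | 57.6 | 44.8 | 34.9 | −22% / −39% |
| 4 rising to 16 at day 3, still 2 at day 12 | 98.0 | 97.9 | 92.2 | 0% / −6% |
| 2 rising to 16 at day 4, plateau to day 6, still 4 at day 12 | 107 | 112 | 112 | +5% / +5% |

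The first four end, or nearly end, within the documents' time frame. The last two outlast it.

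**4. In units of the planned effect.** Bias in SD units = (difference in mean delay in days × points lost per day of delay) / SD of the AUC. The documents give no SD. I assume an SD of 20-50 and a loss of 4-15 points per day. The last column is the two-sided rejection rate with 100 per group and no treatment effect.

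| Difference in mean delay | Loss per day, SD | Bias (SD) | Rejection rate |
|---|---|---|---|
| 6 h | 4, 50 | 0.25 × 4/50 = 0.02 | 5.2% |
| 6 h | 15, 20 | 0.25 × 15/20 = 0.19 | 26% |
| 12 h | 4, 50 | 0.5 × 4/50 = 0.04 | 5.9% |
| 12 h | 12, 30 | 0.5 × 12/30 = 0.20 | 29% |
| 12 h | 15, 20 | 0.5 × 15/20 = 0.375 | 75% |

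A steeper early rise lowers the bottom of the 12 h range. Take 0 at onset, 15 at day 2 and 0 at day 10. The AUC is 72.66 at a half-day delay and 71.25 at one day, a difference of 1.41. With an SD of 70% of the mean (about 50), that is 0.03 SD. So 12 h gives about 0.03-0.38 SD for courses that decline within the window, and nothing or the opposite sign for the slow ones.

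**The case against.** The strongest reply is that D1-D10 is the sensible window. The primary objective concerns a 10-day treatment period, Protocol 8.1.3 itself schedules scoring on D1-D10, and the spray cannot act before V1. This stands: the wording should move to the calculation, not the reverse.

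A reader might infer that the later-presenting group is bound to show a smaller AUC, or that the design favours the spray. The documents support neither.
- Bias needs unequal mean delay, and no delay data are given.
- Nothing links recruitment route to treatment choice. If pre-informed families came earlier and preferred the spray, the expected bias would run against it.
- Protocol section 5 recognises symptoms beyond 10 days, so slow courses cannot be excluded.
- A 12 h gap is large. With delay uniform over 0-48 h (an assumption), the SD is 48/√12 = 13.9 h, so 12 h is 0.87 SD. The standard error of a chance difference at 100 per group is 13.9 × √(2/100), about 2 h.

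Nor does the plan leave illness stage wholly unobserved. SAP 8.4 compares temperature and each symptom score between groups, SAP 10.2.1 offers both to the ANCOVA, and the 48 h cap with the symptom-score ceiling restricts entry to early, milder illness. These are partial proxies: a score at one moment does not show whether the illness is rising or resolving. The ANCOVA is also secondary and, under SAP 6.3.1, descriptive.

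Finally, it would be wrong to say that all six symptom durations are shortened. SAP 10.2.2 starts each at its first symptomatic diary day, so earlier days are lost only for symptoms already present before D1.

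**Conclusion.** The mismatch between definition and calculation is certain from the text and is not declared. The absence of time since onset from every listed baseline description and model is equally clear. That this biases the result is a conditional statement: it requires mean delay to differ between the groups and scores at entry to differ from those nine days later. For the course the protocol describes, later entry is expected to reduce the AUC.

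Neither the size nor the favoured group can be known from the documents. On the assumed declining curves and SDs, a 12 h difference in mean delay is worth about 0.03-0.38 SD; the middle case of 0.20 is half the planned effect of 0.4. A 6 h difference gives 0.02-0.19 SD under the SD and loss ranges in the second table. This should be corrected. It does not show that the comparison is biased, and it does not touch the sample size.

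**What to change.** 1. Reword Protocol 8.1.3 and SAP 10.1 to the WURSS-K AUC over D1-D10 from inclusion, and make the same change where the onset-based label recurs (Protocol synopsis, 9.3 and 9.4; SAP 10.2.1). Declare it in SAP section 12.
2. Record date and time of first symptom at V1, if the eCRF does not already hold it. The investigator needs this information to apply inclusion criterion 3. SAP section 12 reads as though diary data had already been seen; if so, look for onset time in the source files.
3. Tabulate time from onset to D1 by group in SAP 8.4.
4. Force it as a prespecified covariate, outside the stepwise selection, into the AUC ANCOVA and the symptom-duration Cox models.
5. Make this adjusted AUC model the primary analysis, or at least a prespecified sensitivity analysis on which the primary conclusion depends. Adding the covariate only to models that SAP 6.3.1 treats as descriptive would leave the conclusive test exposed.

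The cost is at most one eCRF field, one row in a baseline table, one covariate and some wording. The sample size does not change. Onset time reported by parents is approximate, so the adjustment will be imperfect.

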8.2 Investigational device and comparator

The investigational device which is Healsea® Children. This is a CE marked Medical Device. Patients/parents will be allowed to use or not the investigational nasal spray. If they choose nasal symptoms to be treated with Healsea® Children, they will start the nasal spray treatment following

Page **31** of **61** Version: 2.0; 08 Sep 2021

their inclusion visit (Visit 1). Healsea® Children will be used on the top of conventional therapies for common cold and administered with the help of an adult, spraying one puff (1-2 sec) twice a day in each nostril for 10 days.

No comparator is used in this study. Patient/parents who prefer not to use Healsea® Children will use conventional therapies for common cold only. **However, use of nasal irrigation will not be authorized for these patients.**

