9.1 Descriptive statistics

The cohort is described: continuous variables will be summarized using the mean, standard deviation, median, minimum, maximum and quartiles, categorical variables will be summarized using frequency counts and percentages.

Two groups (called treatment groups for a sake of simplicity) will be extracted from the cohort according to the treatment chosen by the patient and a description of each group will be performed.

Details of the statistical analyses, methods and data conventions will be described in the SAP.

All statistical tests will be 2-sided and performed using a 0.05 significance level.

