9. COMPLIANCE

For patients using Healsea® Children, compliance will be calculated according to the following formula and analysed on the FAS:

$$\text{Compliance (\%)} = \text{Real number of uses} \times 100 / 20$$

With:

- Real number of uses = total number of uses of the treatment from D1 to D10

The number of uses at each day is computed as follows:

- If the patient answered “No” to the question “Did patient use Healsea today?” or “Yes” to the question “Have you not taken Healsea Children today?” then 0;
- If the patient answered “Yes” to the question “Did patient use Healsea today?” then:
 - o If the patient answered “Yes” to the question “Did patient use Healsea once a day?” then 1;
 - o If the patient answered “Yes” to the question “Did patient use Healsea more than twice a day?” then 3;
 - o If he/she did not answer “Yes” neither to the question “Did patient use Healsea once a day?” nor to the question “Did patient use Healsea more than twice a day?” nor to the question “Have you not taken Healsea Children today?” then 2.

Compliance will be described only on Healsea® Children arm.

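### No WURSS-K is scheduled before the first spray, so a self-selected comparison has no pre-treatment value on the primary outcome's own scale

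*Protocol*

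**What the plan says.** Protocol 8.1.3 defines the primary endpoint and its timing: "the patient will score the WURSS-K daily in the evening, taking in account the symptoms from the morning to the evening, during D1-D10". The flow charts in the protocol and the SAP mark the WURSS-K in the at-home columns and not at Visit 1.

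For families who choose the device, Protocol 8.2 says "they will start the nasal spray treatment following" the inclusion visit, which is Day 1. SAP section 9 expects use on that day: "Real number of uses = total number of uses of the treatment from D1 to D10", divided by 20, which is two uses a day for ten days.

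At Visit 1 (Protocol 8.3.11) staff are to "Review and detail the questions of the WURSS-K", but no score is recorded. They do "Record the score of the common cold symptoms (headache, muscle ache, chilliness, sore throat, blocked nose, runny nose, cough, sneezing according a physician-rated symptom score", each item rated 0 to 3. Eligibility (8.3.1.1) caps that total: "cough, sneezing with a total score ≤9".

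Groups are formed "according to the treatment chosen by the patient" (Protocol 9.1). Section 8.1.2, on measures against bias, reads "Not applicable".

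The primary test is an unadjusted t-test or Wilcoxon test (Protocol 9.3, SAP 10.1), and SAP 6.3.1 makes only that result conclusive. Baseline temperature and the symptom scores are compared between groups (SAP 8.4). They are also the listed confounders in the secondary models, under stepwise selection at 0.20 (SAP 10.2). SAP 6.4.6 computes the AUC from D1 to D10.

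**The concern.** When families choose the treatment, how ill the child feels at the start can influence both the choice and the later symptom curve. The natural control for this is a pre-treatment value of the outcome itself, from the same reporter on the same scale, and the plan has none.

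The D1 evening entry cannot fill that role. It comes after an open-label choice, it may come after the first spray, and it counts in the AUC, so adjusting for it would adjust for part of the outcome.

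The physician score is a different instrument with a different rater. It has nothing on function, and the functional items make up half of the WURSS-K total. Two things are at stake: residual confounding by initial severity, and precision that an outcome-scale baseline would supply.

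**Working it through.** **Plan's own figure.** Protocol 7.4 and SAP section 4: d = 0.4, two-sided 5%, 80% power, 100 per group. The t-based calculation needs 99.1 per group, and 100 per group gives 80.4% power. The figure reproduces.

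**Coverage of the existing baseline.** Items are from Protocol 8.1.3 and 8.3.11.

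| WURSS-K items | Number | Points | In physician score? |
|---|---|---|---|
| Runny nose, stuffy nose, sneezing, sore throat, cough | 5 | 15 | Yes |
| Feeling tired | 1 | 3 | No |
| Functional items | 7 | 21 | No |
| Global severity | 1 | 3 | No |

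Uncovered: 1 + 7 + 1 = 9 of 14 items, and 9 × 3 = 27 of 42 points. The physician score's other three items (headache, muscle ache, chilliness) are not in the WURSS-K. Its total at entry is limited to 9 of a possible 24 (8 × 3).

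**Assumed quantities.** The documents give none of these:
- r: correlation of a baseline WURSS-K with the AUC.
- q: correlation of the physician score with a baseline WURSS-K. The physician score is taken to predict the AUC only through the baseline WURSS-K, so its own correlation with the AUC is r × q.
- b: baseline gap between the groups, in SD of the baseline WURSS-K.

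**Precision.** Adjusting for a covariate that correlates ρ with the AUC gives an effective d of 0.4/√(1 − ρ²), with 100 per group. At r = 0.5:

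| Adjustment | ρ | Effective d | Power |
|---|---|---|---|
| None | 0 | 0.400 | 80.4% |
| Physician score, q = 0.5 | 0.25 | 0.413 | 82.8% |
| Physician score, q = 0.7 | 0.35 | 0.427 | 85.2% |
| Baseline WURSS-K | 0.50 | 0.462 | 90.1% |

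The gain over the existing covariate is 90.1 − 85.2 = 4.9 to 90.1 − 82.8 = 7.3 points. The same formula at r = 0.3 gives 81.2–82.1% with the physician score and 83.9% with a baseline WURSS-K. At r = 0.7 it gives 85.2–89.8% and 97.6%. The gain therefore depends strongly on r.

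**Bias with no true effect.** The unadjusted shift in the AUC is r × b. Adjusting for the physician score removes its slope (r × q) times its gap (q × b), which leaves r × b × (1 − q²). At r = 0.5 and b = 0.2:
- Unadjusted: 0.5 × 0.2 = 0.10 SD, which is 0.10/0.4 = 25% of the design effect. With a standard error of √(2/100), the two-sided rejection rate is 10.9% instead of 5%.
- Physician score, q = 0.5: 0.10 × 0.75 = 0.075 SD, rejection rate 8.5%.
- Physician score, q = 0.7: 0.10 × 0.51 = 0.051 SD, rejection rate 6.7%.

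At b = 0.3 the shifts are 0.15, 0.112 and 0.076 SD, with rejection rates of 18.6%, 13.0% and 8.9%.

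**The case against.** Baseline severity is not unmeasured. Temperature and eight symptom scores are recorded, compared between groups and offered to the adjusted models, and five of the eight symptoms match WURSS-K items. A reader might infer that the adjusted analysis cannot remove a severity difference at all. The documents do not support that: these covariates can remove part of it. The entry limits (onset within 48 hours, total score of 9 or less) also narrow the spread of severity. This objection stands, and it is why the size of the problem must be measured against the physician score and not against no adjustment.

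A reader might also infer that every treated child's D1 score is post-spray. The order of first spray and first diary entry is not fixed, and the entry looks back over hours before the spray. A child who obtained the spray late could score first. That would be chance, though, and the score would still follow the choice and still count in the AUC.

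A third tempting reading is that adding the form would by itself lift the primary test's power to about 90%. It would not, because the primary test takes no covariate and all other p-values are for information only.

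Finally, this is a design preference and not a contradiction in the plan. SAP section 12 already describes patients' diary answers, so by that stage the form could no longer be added for children already followed.

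**Conclusion.** The point holds as a modest, inexpensive improvement to the design. No WURSS-K is scheduled before the first spray, and the existing baseline covers 15 of the 42 outcome points. Adjustment for initial severity can therefore be only partial.

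At r = 0.5, a baseline WURSS-K would add about 5 to 7 percentage points of power over the physician score. With a baseline gap of 0.2 SD, bias of about 0.05 to 0.075 SD remains after physician-score adjustment, compared with 0.10 SD in the unadjusted primary test. All values of r, q and b are assumptions, and the documents do not show which group, if either, would start out sicker. The planned 200 children remain sufficient. A baseline WURSS-K would not remove confounding from unmeasured causes or bias from open-label self-report.

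**What to change.** In Protocol 8.3.11 and the flow chart, have the child complete the WURSS-K once at Visit 1, before the treatment choice is recorded and before any spray. The visit list now puts the choice ahead of the review of the form, so that order would change. State the recall window: the printed form asks about the time since yesterday, whereas the diary covers morning to evening.

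In the SAP, keep this score out of the AUC. Enter it as a forced covariate in the AUC ANCOVA of section 10.2.1, exempt from stepwise selection. Make that ANCOVA the primary analysis in Protocol 9.3 and SAP 10.1, since otherwise the gain does not reach the conclusive result. Do not use the D1 evening score as a baseline.

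The cost is a few minutes at a visit where the form is already explained, plus one e-CRF form, with no extra staff. For children already enrolled, the value cannot be recovered, and the report should state this as a limitation.
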